6.10 Supportive Therapy

- 6.10.1** All patients will be adequately hydrated and receive appropriate anti-emetics based upon institutional guidelines.
- 6.10.2** Additional growth factors may be used according to institutional practice guidelines or the preference of the attending physician.
- 6.10.3** Antimicrobial prophylaxis should be used according to institutional practice guidelines. In case of neutropenic fever, standard diagnostic testing will be performed, and empiric antibiotic coverage will be utilized as per usual care and standard institutional practices.
- 6.10.4** Transfusional support should be carried out according to institutional practice guidelines.

6.11 Treatment of CNS Disease

Treatment of CNS disease is done according to institutional practice guidelines or the preference of the attending physician.

6.12 Recommended Follow-up Care

After completion of protocol treatment, patients should be evaluated by treating physicians according to institutional and/or national guidelines or the discretion of the attending physician. These evaluations may include peripheral blood studies and/or bone marrow examinations, as clinically indicated.

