6.6 Consolidation Therapy

After achievement of a CR/CRI (irrespective of MRD) with 1-2 courses of G-CLAM therapy, patients are eligible for post-remission therapy with G-CLA.

- 6.6.1 The treatment is identical to the induction course but without mitoxantrone (i.e. G-CSF, cladribine, and cytarabine, or “G-CLA” at same dose level as induction). If a patient had excessive toxicities (grade ≥ 3 non-hematologic toxicity excluding neutropenic fever and infections) during induction, a dose reduction can be considered as described in sections 6.8 and 6.9, as well as APPENDIX B.
- 6.6.2 Post-remission courses should start within 6 weeks of achieving CR/CRI once patients have recovered to \leq Grade 2 toxicities from the previous course of therapy.
- 6.6.3 Patients on the higher-dose arm can receive up to 4 courses of consolidation therapy.
- 6.6.4 Patients on the lower-dose arm can receive up to 12 cycles of consolidation therapy.
- 6.6.5 Patients can proceed to transplantation barring contraindications and if a suitable donor is available.

6.7 **Monitoring during/after Induction and Consolidation Therapy**

For patient monitoring, the following studies and study intervals are suggested and will be performed at the physician's discretion:

- 6.7.1 Complete blood counts with differential blood count, including immature cells/blast, and platelet count at least 2 times weekly until ANC >500/ μ L and then at least weekly until platelet count >100,000/ μ L.
- 6.7.2 Metabolic panel, including bilirubin, ALT/AST, and creatinine at least weekly until ANC >1,000/ μ L and platelet count >100,000/ μ L.
- 6.7.3 If patients develop signs or symptoms suggestive of cardiac dysfunction, LVEF should be assessed using the same method to evaluate baseline LVEF status (MUGA scan or echocardiography, or other appropriate diagnostic modality).

6.8 **Dose Modifications of Chemotherapeutic Drugs for Induction or Subsequent Treatment Cycles for Higher-Dose Arm**

For patients who have organ dysfunction at baseline—defined as a serum creatinine > 2.0 mg/dL or a bilirubin concentration is $\geq 3 \times$ IULN— or those who experienced \geq Grade 3 non-hematologic toxicities excluding neutropenic fever and infections during the first induction, a dose reduction can be considered as follows (see also APPENDIX B):

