7.4.6 Storage and Stability: Mitoxantrone should be stored between 15°C - 25°C (59°F-77°F)

8.0 EVALUATION AND END POINT DEFINITIONS

8.1 Treatment Response and Outcome

Treatment response (e.g. morphologic/cytogenetic/molecular CR/CRi) or treatment failure (e.g. resistant disease, aplasia, morphological or molecular/cytogenetic relapse) as well as treatment outcome (e.g. overall survival, relapse-free survival, event-free survival, and remission duration) will be determined by peripheral blood count and bone marrow evaluation as per Section 6.5 and categorized according to criteria recommended by International Working Groups.^{17,18} Patients are routinely assessed for the presence of minimal residual disease (MRD) as detected by multi-parameter flow cytometry and cytogenetic assessment, as per institutional practice.

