10.2 Duration of Follow-up

Patients will be followed after completion of study treatment to determine event free survival (EFS) and relapse-free survival ([RFS] (for patients achieving CR), as well as overall survival (for all patients) for a maximum of 5 years. Follow-up may include periodic (e.g. every 3 months) review of medical records, and, if absolutely necessary, direct contact of the study participant.

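### Relapse may be dated earlier in the lower-dose arm at equal true relapse times, because consolidation can last 12 courses against 4 and no common relapse-assessment schedule is set

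*Combined protocol and SAP*

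**What the plan says.** All references are to the combined protocol and SAP.

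- **On courses.** Section 6.7 covers monitoring during and after induction and consolidation. It lists "Complete blood counts with differential blood count, including immature cells/blast, and platelet count at least 2 times weekly" until neutrophil recovery, then at least weekly until platelet recovery. Its opening sentence makes this advisory: "the following studies and study intervals are suggested and will be performed at the physician's discretion".
- **Length of consolidation.** Section 6.6.3: "Patients on the higher-dose arm can receive up to 4 courses of consolidation therapy". Section 6.6.4: "Patients on the lower-dose arm can receive up to 12 cycles of consolidation therapy".
- **After protocol treatment.** Section 6.12 refers to guidelines or the attending physician's discretion and adds: "These evaluations may include peripheral blood studies and/or bone marrow examinations, as clinically indicated". No interval is given.
- **Long-term follow-up.** Section 10.2: "Follow-up may include periodic (e.g. every 3 months) review of medical records", for up to 5 years.
- **How outcomes are determined.** Section 8.1 says that response and outcome, including RFS, EFS and remission duration, "will be determined by peripheral blood count and bone marrow evaluation as per Section 6.5". Section 6.5 schedules only the assessment after the first induction course.
- **Use.** Objective 2.2.3 compares duration of response between the treatment intensities. Section 14.3.2 item 3 estimates the difference, to inform a later, larger study.

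**The concern.** A relapse is recorded when a test finds it, so its date depends on how often tests are done. Here the period with a suggested short interval is tied to courses, and its maximum length is three times greater in one arm (12 / 4 = 3). Between the end of the fourth course and the end of the twelfth, a lower-dose patient may still be having counts around each course, while a higher-dose patient is under section 6.12 with no stated interval.

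The assigned regimen creates this difference, so neither randomization nor a larger sample removes it. If it occurs, duration of response, RFS and EFS would look somewhat longer in the higher-dose arm for reasons unrelated to the drugs. Those estimates are meant to feed the design of the next trial. Unless the last relapse-free date is recorded, the analysis cannot separate later relapse from later detection.

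**Working it through.** The plan states no figure for relapse timing, so there is none to reproduce. The check asks how far apart the recorded dates would be if the true relapse hazard were the same in both arms.

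**Inputs from the documents.** Ceilings of 4 and 12 courses (6.6.3, 6.6.4); weekly counts as the sparser of the two suggested on-course intervals (6.7); follow-up to 5 years (10.2); 12-month RFS of 62% in the earlier G-CLAM cohort of medically fit adults (1.0); up to 50 patients (14.2).

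**Assumptions not in the documents.** One month per course; every patient reaches the ceiling; checks every 1 or 3 months after treatment; exponential relapse times with 12-month RFS of 62% or, for a less fit population, 40%.

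**Step 1: relapses affected.** Only those between months 4 and 12 of remission can be dated differently in that window. The share is S(4) − S(12), with S(t) = S(12)^(t/12).
- At 40%: 0.737 − 0.400 = 0.337.
- At 62%: 0.853 − 0.620 = 0.233.

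**Step 2: dating delay.** With checks every d months the average delay is about d/2.
- Lower-dose arm, weekly (d = 0.25): about 0.13 month.
- Higher-dose arm, monthly: about 0.5 month. Difference about 0.4 month.
- Higher-dose arm, 3-monthly, so checks at months 7, 10 and 13: the mean delay is 1.5 months for relapses in months 4-7 and 7-10, and 2.0 for months 10-12. Weighted by length, (3 × 1.5 + 3 × 1.5 + 2 × 2.0) / 8 = 1.63. Simulation with 2,000,000 patients gives 1.64-1.65. Difference about 1.5 months.

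**Step 3: average RFS gap over months 4-12.** This is roughly share × delay difference / 8, less any delay that runs past month 12.
- Monthly: 0.233 × 0.38 / 8 = 1.1 points (62%); 0.337 × 0.38 / 8 = 1.6 points (40%).
- 3-monthly: 0.233 × 1.51 / 8 = 4.4 points and 0.337 × 1.52 / 8 = 6.4 points before cutting at month 12. Simulated with the cut: 3.7 and 5.6 points.

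**Step 4: over 5 years.** The apparent relapse rate (events / person-time), lower-dose over higher-dose, is 1.00 (62%, monthly) to 1.04 (40%, 3-monthly).

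**Step 5: other settings.** A second simulation used 4- or 6-week courses, median time to relapse of 6, 10 or 15 months, and checks every 1, 2 or 3 months after treatment.
- With weekly on-course counts, the dating difference averaged over all relapses is 0.4-2.4 weeks, and the apparent hazard ratio is 1.00-1.10.
- With only one effective check per course and monthly checks afterwards, the difference inside the window is +0.2 week (4-week courses) or about −0.9 week (6-week courses, reversed).
- With the same interval on and off treatment it is 0.

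**Step 6: patients involved.** Take 25 per arm and a remission rate of 22% (the MRD-negative CR rate in the control data of section 14.4) to 50% (assumed). That gives 5.5 to 12.5 patients in remission. With 24-38% of relapses in the window (second simulation), 5.5 × 0.24 = 1.3 to 12.5 × 0.38 = 4.8, so about 1-5 relapses per arm.

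**The case against.** The strongest reply is that the documents do not fix any of the conditions the effect needs.

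- The counts in section 6.7 are suggested and discretionary, and the suggestion lapses once counts recover within a course. The contrast is a suggested interval against none, not mandatory against optional testing. This stands.
- The 3-month figure in section 10.2 is an example interval for reading records. A record review retrieves the actual date of a relapse found in between, so it is not a detection interval. This also stands: 3-monthly checking is one end of an assumed range, not the plan's schedule.
- Four and twelve are ceilings. Transplant (6.6.5), toxicity and relapse (10.1) end courses sooner. The lower-dose induction limit is also inconsistent (2 courses in 6.5.3, 6 in 6.0 and 10.1.4), which affects time on courses; those passages must be reconciled.
- The comparison is exploratory and declared unpowered (14.3.2), and patients may choose their arm (14.1), so comparisons that pool them with randomized patients are confounded anyway. This limits the importance of the point. It does not answer it, because estimation is the stated aim and unequal detection is bias, not imprecision.

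A reader might infer that relapse will necessarily be dated earlier in the lower-dose arm, or that RFS will differ markedly. The documents support neither. An RFS gap read just before a simulated 3-monthly check is near its widest and unrepresentative: in the 40% case it is nil at 10.0 months and reversed at 13.0 months (37% higher-dose, 40% lower-dose).

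**Conclusion.** The point holds in conditional form. No section puts the two arms on a common schedule for finding relapse, and the regimen-dependent ceilings make earlier dating in the lower-dose arm possible at equal true relapse times. If all patients reach the ceilings with weekly on-course counts, the size is as in steps 2-4, which is close to an upper range for those inputs because early stopping reduces it. Sparser on-course checking can remove or slightly reverse it.

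Severity is minor. Duration of response, RFS and EFS are exploratory, and few relapses per arm are involved. The feasibility endpoint, 28-day mortality, the MRD-negative CR monitoring rule and overall survival do not depend on relapse dates.

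**What to change.** - **Section 10.2:** for each relapse, abstract the date of the last relapse-free assessment as well as the first positive one.
- **Section 14.3.2 item 3:** analyse relapse-based outcomes as interval-censored between those two dates, at least as a sensitivity analysis, with deaths dated exactly. Keep overall survival as the main time-to-event comparison.

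In the simulation above, an interval-censored exponential fit, in which each relapse contributes S(last negative) − S(first positive), returns the true hazard in both arms (ratio to truth 1.00 in each).

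Rounding each relapse to the end of the 3-month interval in which it was documented is not a substitute. With 3-monthly checks, a month-5 relapse is documented at month 5 in the lower-dose arm and rounded to 6; in the higher-dose arm it is documented at 7 and rounded to 9. The average difference for month 4-12 relapses rises from 1.5 to 2.3 months.

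The cost is a sentence in each section, one more abstracted date per relapse, and less precise relapse times. One limit remains: interval-censoring assumes that the timing of checks does not depend on the relapse itself, which holds only approximately when tests are prompted by symptoms.

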7.0 INFORMATION ON STUDY DRUGS

G-CSF, cladribine, cytarabine, and mitoxantrone will be obtained commercially.

7.1 Drug Information on G-CSF (Granulocyte colony-stimulating factor)

- 7.1.1** Mechanism of Action: G-CSF is a growth factor that stimulates the production, maturation, and activation of neutrophils. Further, it promotes premature release of neutrophils from the bone marrow and enhances their phagocytic capacity.
- 7.1.2** Pharmacokinetics: Peak G-CSF concentrations after sub-cutaneous dosing occur in 2 to 8 hours, though the onset of action is approximately 24 hours, with plateau concentrations in 3-5 days, and elimination over an 11-20 day period. G-CSF is cleared by systemic degradation. Notably, as G-CSF binds neutrophils, plasma levels are controlled in large part by the absolute neutrophil count.
- 7.1.3** Adverse Effects (AEs): *Common drug-related AEs (occurring in >10% of patients)* include fever, petechiae, elevated uric acid, splenomegaly, bone pain, and epistaxis. *Less common drug-related AEs (occurring in 1% -10% of patients)*

include hyper- or hypotension, arrhythmias, headache, nausea, vomiting, leukocytosis, and transfusion reaction. *Infrequent drug-related AEs (occurring in <1% of patients)* include acute respiratory distress syndrome, allergic reactions, alopecia, alveolar hemorrhage, arthralgia, bone density decrease, capillary leak syndrome, cerebral hemorrhage, vasculitis, dyspnea, edema, erythema nodosum, hematuria, hemoptysis, hepatomegaly, hypersensitivity, injection site reaction, pericarditis, proteinuria, psoriasis exacerbation, pulmonary infiltrates, renal insufficiency, sickle cell crisis, splenic rupture, Sweet's syndrome, tachycardia, and thrombophlebitis.

7.1.4 Recommended dose adjustments for organ dysfunction: There is limited or no data examining the toxicity of G-CSF in patients with renal or liver dysfunction. Therefore, administration of G-CSF to patients with liver or kidney disease must be done with caution.

7.2 **Drug Information on Cladribine (2-chloro-2'-deoxyadenosine, 2-CdA)**

7.2.1 Mechanism of Action: Cladribine is a prodrug that is converted to an adenosine deaminase-resistant triphosphate derivative (2-CdATP). This molecule is then activated by deoxycytidine kinase to a 5'-triphosphate derivative (2-CdAMP), which is incorporated into DNA where it acts as a transcription regulator. In addition to its cytotoxic properties in dividing cells, cladribine induces death in quiescent cells of lymphoid origin through an unknown mechanism.

7.2.2 Pharmacokinetics: Cladribine is renally excreted, with 18-35% as unchanged drug. It is able to penetrate the CSF, where it achieves 25% of plasma concentrations. It is 20% protein-bound. The half-life for elimination after a 2-hour infusion is 6.7 ± 2.5 hours in patients with normal renal function.

7.2.3 Adverse Effects: *Common adverse effects (occurring in >10% of patients)* include fever, fatigue, headache, rash, nausea, anorexia, vomiting, myelosuppression (including grade 3/4 neutropenia/thrombocytopenia), injection site reaction, and infection. *Less common adverse effects (occurring in 1 to 10% of patients)* include edema, tachycardia, thrombosis, chills, dizziness, insomnia, malaise, diarrhea or constipation, weakness, myalgias and arthralgias, cough, dyspnea, epistaxis, and diaphoresis. *Rare adverse effects (occurring in <1% of patients)* include aplastic anemia, bacteremia, opportunistic infections, lymphocytopenia, altered mental status, hemolytic anemia, hypersensitivity, myelodysplastic syndrome, quadripareisis, and renal dysfunction/failure.

7.2.4 Reconstitution: Cladribine is supplied as a sterile, preservative-free, isotonic solution containing 10 mg of cladribine (1 mg/mL) in 10 mL single-use vials. Cladribine should be passed through a sterile 0.22 μ m filter prior to introduction into the infusion bag containing 0.9% Sodium Chloride Injection, USP.

7.2.5 Administration and Compatibility: The use of 5% dextrose is not recommended as a diluent because of increased degradation of cladribine. The infusion solution is stable for 24 hours at room temperature.

7.2.6 Storage and Stability: Store refrigerated 2° to 8°C (36° to 46°F). Protect from light during storage.

7.2.7 Recommended Dose Adjustments for Organ Dysfunction: Specific guidelines for cladribine dosing in patients with hepatic/renal dysfunction or hypoalbuminemia are not clearly defined. Because of the potential for compensatory elimination of cladribine in patients with hepatic and/or renal dysfunction, specific guidelines for dosing are difficult to define. Thus, when deciding whether to adjust cladribine doses for renal dysfunction, the risks for potential toxicities (e.g., myelosuppression, neurotoxicity) against the benefits and goals of treatment must be considered.

7.3 Drug Information on Cytarabine (Cytosine arabinoside)

7.3.1 Mechanism of Action: Cytarabine is a synthetic pyrimidine analog, in which the sugar moiety (normally a ribose or deoxyribose) has been replaced with arabinose. Although its mechanism of action is not completely understood, the active form of cytarabine is probably incorporated into the DNA and interferes with DNA synthesis. As such, cytarabine has been found to primarily effect dividing cells, blocking their progression from G₁ to S phase.

7.3.2 Pharmacokinetics: Cytarabine is metabolized by deoxycytidine kinase and other kinases into its most active form (aracytidine triphosphate). Aracytidine triphosphate is converted to nontoxic uracil derivatives by pyrimidine nucleoside deaminases. This balance between the levels of kinases and deaminases is critical for regulating the sensitivity/resistance of cells to the drug. The plasma clearance of cytarabine is biphasic, with an initial rapid phase and more prolonged second clearance phase. The rapid clearance phase has a relatively short half-life ($t_{1/2\alpha} = 10$ minutes), while the half-life of the second clearance phase is slightly longer ($t_{1/2\beta} = 1 - 3$ hours). The nontoxic metabolites from the drug are excreted in the urine, and within 24 hours after the infusion, approximately 80% of these nontoxic metabolites can be recovered from the urine.

7.3.3 Adverse Effects: The dose-limiting toxicity for cytarabine is myelosuppression. *Adverse Events Associated with Standard Dose Cytarabine: Frequent AEs (not definitely quantified)* include the following: myelosuppression (leucopenia, anemia, neutropenia, thrombocytopenia), pyrexia, rash, anorexia, diarrhea, nausea, vomiting, mucositis, anal inflammation or ulceration, hepatic dysfunction or increased liver enzymes, and local thrombophlebitis. *Less frequent AEs (not definitely quantified)* include chest pain, pericarditis, dyspnea, dizziness, headache, neural toxicity, neuritis, alopecia, pruritis, skin freckling, skin ulceration, urticaria, abdominal pain, bowel necrosis, esophageal ulceration, esophagitis, pancreatitis, sore throat, urinary retention, jaundice/hyperbilirubinemia, local site cellulites, renal dysfunction, allergic edema or anaphylaxis, sepsis, and sudden respiratory distress syndrome. *Infrequent AEs (not definitely quantified)* include aseptic meningitis, cardiopulmonary arrest, cerebral dysfunction, cytarabine syndrome (bone pain, chest pain, conjunctivitis, fever, maculopapular rash, malaise, myalgia), exanthematous pustulosis, hyperuricemia, intestinal pneumonitis, increased lipase, paralysis with intrathecal and IV combination therapy, rhabdomyolysis, veno-occlusive disorder, and death. *Adverse Events Associated with High Dose Cytarabine* include cardiomegaly and

cardiomyopathy, coma, severe neurotoxicity, personality change, somnolence, total body alopecia, severe rash or skin desquamation, gastrointestinal ulceration, peritonitis, intestinal pneumatosis, necrotizing colitis, liver abscess or damage, peripheral neuropathy, corneal toxicity, hemorrhagic conjunctivitis, pulmonary edema, sudden respiratory distress syndrome, and sepsis.

7.3.4 Reconstitution: Cytarabine should be reconstituted in sterile water and can be further diluted using either 5% dextrose or sodium chloride solutions into appropriate concentrations for infusion.

7.3.5 Administration and Compatibility: The diluted cytarabine solution should be inspected for particulate matter, discoloration, and haze prior to infusion. If there is evidence of particulate matter, discoloration, or haze the solution should not be infused. Patients should be medicated with standard anti-emetic therapy. Cytarabine is not compatible (1) during Y-site administration with allopurinol, amphotericin B, ganciclovir; (2) in syringe with metoclopropamide; or (3) admixed with fluorouracil, heparin, insulin (regular), nafcillin, oxacillin, penicillin G. Cytarabine may have variable compatibility when admixed with gentamycin, hydrocortisone, and methylprednisolone.

7.3.6 Storage and Stability: Vials of non-reconstituted cytarabine should be stored at room temperature 15°C - 30°C (59°F - 86°F). The diluted cytarabine solution may be stable for up to 48 hours if stored at room temperature.

7.3.7 Drug-Drug Interaction: Reversible decreases in the plasma steady-state concentration for digoxin and cardiac glycosides may occur. Cytarabine may diminish the therapeutic effect of flucytosine. There is *ex vivo* data suggesting that cytarabine may reduce the effectiveness gentamycin for killing *K. pneumoniae*.

7.3.8 Warnings and Precautions: *Ex vivo* and *in vivo* studies have found that cytarabine causes extensive chromosomal damage and potential malignant transformation. Although there have been some case reports describing cytarabine use in pregnant humans, these cases reports are few. Thus, cytarabine is considered Pregnancy Category D. Women should be advised not to become pregnant while receiving cytarabine, and men should be advised not to father a child while receiving cytarabine and for at least 3 months after completing the therapy. It is not known whether cytarabine or its metabolites are excreted in breast milk; thus, it is not recommended for lactating females who are breast-feeding. As with any highly immunosuppressive medication, cytarabine may diminish the effectiveness of dead and live vaccines and enhance the toxic/adverse effect of live vaccines. One should avoid use of live vaccines while receiving it. A small percentage of patients will have a hypersensitivity reaction to cytarabine, and these individuals should not receive the drug again.

7.3.9 Recommended Dose Adjustments for Organ Dysfunction: Guidelines for adjusting cytarabine dose due to renal or liver dysfunction are not standardized, but many clinicians will adjust the dose based upon the function of these organs.

